4.3 Primary and secondary outcome measures

4.3.1 Primary

Number of ICU patients with delirium intervened with haloperidol (N05AD01)

(Definition: Patients receiving one or more doses of haloperidol and are described as delirious. Delirium defined as below in secondary outcome 2).

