6.1 Patient evaluation

Baseline patient characteristics

1. Age on the day of ICU admission (years)

2. Gender (male/female)
3. Simplified Acute Physiology Score II (SAPS II) within the first 24 hours of the ICU admission (0-163 points)
4. Use of dialysis, vasopressors or inotropes (noradrenaline (C01CA03), adrenaline (C01CA24), dobutamine (C01CA07), dopamine (C01CA04), milrinone (C01CE02), levosimendan (C01CX08) vasopressin (H01BA01) or phenylephrine (C01C A06) and/or medical ventilation (y/n)
5. Days admitted in the hospital prior to ICU admission (number of days)
6. Type of admission diagnose (sepsis y/n, trauma y/n, surgery 24 hour prior to admission y/n, elective surgery y/n, emergency surgery y/n)
7. Treatment with antipsychotics (N05A), anti-Parkinson (N04), antidepressant (N06A) and benzodiazepine (N05BA) prior to hospital/ICU admission
8. Risk factor status prior to hospital/ICU (*Previous delirious episodes defined as: patients receiving one or more doses of haloperidol, AND described as delirious (documented CAM-ICU positive or ICDSC ≥ 4 point (0-8 point) or DOS >3 point (0-13/day point), ICD-10 code (DF05, DF050, DF058), or agitated and/or not cooperative and/or eyes open and big with no contact (Glasgow Coma Score (GCS) > 7) and/or anxiety, or restrained to the bed), smoking more than 10 cigarettes a day yes/no, alcohol abuse more than 3 units (1 units defined as 12 g of alcohol) a day yes/no)*)
9. Hearing or vision impairment (y/n)

Daily data collection from admission through last day of follow-up (discharge from ICU or day 90

10. Sedation assessment (the sites will only register the score (a, b or c) they use in clinical practice), as described in patient files, one score equals one positive day with sedative induced coma.
 - a. RASS score -3- (-5) (y/n) at any time during the day or
 - b. Ramsey sedations score 4-6 points (y/n) at any time during the day or
 - c. MASS score 1-0 (y/n) at any time during the day
11. Coma assessment, as Glasgow Coma Scale (GCS) score without any sedation
 - a. GCS < 8 point (y/n) at any time during the day
12. Delirium assessment (the sites will only register the score (a, b or c) they use in clinical practice), as described in patient files, one positive score equals one delirium day. (appendix 2)
 - a. CAM-ICU (positive /negative/UTA, Unable To Assess)
 - b. ICDSC ≥ 4 point (0-8 point)
 - c. DOS >3 point (0-13 point)
 - d. ICD 10 code DF05, DF050, DF058

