13. Subtype description of delirium (hypo, hyper or mixed¹⁴)
14. Restrained to the bed (y/n)
15. Treatment with continuous vasopressor or inotropes at any time during this day (noradrenaline (C01CA03), adrenaline (C01CA24), dobutamine (C01CA07), dopamine (C01CA04), milrinone (C01CE02), levosimendan (C01CX08), phenylephrine (C01C A06) or vasopressin (H01BA01))
16. Use of invasive mechanical ventilation (y/n) or use of non-invasive ventilation at any time during this day (y/n)
17. Is the patient sedated at any time during this day (y/n), with continuous infusion of
 - a. Propofol (N01AX10)
 - b. Midazolam (N05CD08)
 - c. Dexmedetomidine (N05CM18) (continues > 18 hours pr./day or continuous > 4 hours between 10 pm – 06 am)
 - d. Other

18. Pain management with intravenous opioid infusion for more than 2 consecutive hours at any time during this day (y/n).
 - a. Remifentanyl (N01AH06)
 - b. Sufentanyl (N01AH03)
 - c. Fentanyl (N01AH01)
 - d. Morphine (N02AA01)
19. Pharmacologic intervention for delirium (first initial dose will be recorded, then the 24 hour accumulated verified administrated dose. Is treatment prescribed as fixed or per need or both)
 - a. Antipsychotics
 - i. Haloperidol (N05AD01) (mg/day) (prophylaxis y/n)(regular dosing mg/day or as needed mg/day)
 - ii. Olanzapine (N05AH03) (mg/day) (prophylaxis y/n)(regular dosing mg/day or as needed mg/day)
 - iii. Quetiapin (N05AH04) (mg/day) (prophylaxis y/n)(regular dosing mg/day or as needed mg/day)
 - b. Anxiolytics
 - i. Benzodiazepine (N05BA) (y/n)
 - ii. Rivastigmin (N06DA03) (y/n)
 - iii. Other (y/n)
 - c. Hypnotics and sleeping pills (y/n) if any of the below.
 - i. Zopiclon (N05CF01)
 - ii. Zolpidem (N05CF02)
 - iii. Triazolam (N05CD05)
 - iv. Lormetazepam (N05CD06)
 - v. Nitrazepam (N05CD02)
 - vi. Chloralhydrate (N05CC01)
 - vii. Melatonin (N05CH01)
 - viii. Promethazine (R06AD02)
 - ix. Other

Day 90 after ICU admission

20. Vital status (dead/alive) (if relevant, date of death)
21. Discharged from ICU (Y/N and date)
22. Discharge from hospital (Y/N and date)

6 month after ICU admission

23. Cognitive impairment assessment with RBANS (40 to 160 points)

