7.3 Statistical plan

The number of patients receiving haloperidol (totally and regularly, as needed and mixed dosing) will be presented as frequencies (% with 95% confidence intervals). Numeric data will be given as medians (interquartile range [IQR]). We will compare differences in baseline characteristics using non-parametric tests between patients who receive haloperidol and patients who do not receive haloperidol. To assess risk factors for the use of haloperidol, we will do multivariate analyses including patient characteristics (age, dialysis, shock and mechanical ventilation and delirium in the first 24 h of admission) and ICU characteristic (university hospital, guidelines for identifying and/or treating delirium and average staff-patient ratio). To assess if haloperidol is an independent predictor of 90-day mortality, we will do multivariate analysis including patient characteristics (age, dialysis, shock and mechanical ventilation and delirium in the first 24 h of admission) and time. We will do exploratory analyses on the interaction between delirium and use of haloperidol and the patient-relevant outcomes measure (mortality, days alive without mechanical ventilation and days alive and out for hospital). All statistical tests will be 2-tailed and $p < .05$ considered statistically significant.

8. Data Handling

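### The haloperidol–mortality model in section 7.3 controls only for delirium in the first 24 hours and leaves out the collected SAPS II, so its haloperidol estimate can be biased in either direction

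*Protocol*

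**What the plan says.** Section 7.3 gives the purpose of the model as follows: "To assess if haloperidol is an independent predictor of 90-day mortality, we will do multivariate analysis including patient characteristics". The covariates are then written out as "age, dialysis, shock and mechanical ventilation and delirium in the first 24 h of admission) and time". The time term is not defined. The form in which haloperidol enters the model (ever/never, dose, or from first dose onwards) is not stated.

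Other sections fix the setting of this model:

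- **Exposure.** Section 4.3.1 defines haloperidol use as "Patients receiving one or more doses of haloperidol and are described as delirious", with no limit on when after admission the dose is given.
- **Outcome.** Section 4.3.2 counts 90-day mortality from ICU admission.
- **Population.** Section 7.2 analyses all acute admissions, so untreated patients include those who never become delirious.
- **Severity.** Section 6.1, item 3, collects "Simplified Acute Physiology Score II (SAPS II) within the first 24 hours of the ICU admission (0-163 points". Section 7.3 does not use it in this model.
- **Daily data.** Section 6.1 plans "Daily data collection from admission through last day of follow-up (discharge from ICU or day 90". This covers delirium, coma and haloperidol; for the drug, "first initial dose will be recorded, then the 24 hour accumulated verified administrated dose".

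**The concern.** Delirium is the reason for giving haloperidol, and section 2.1 itself reports that delirium in ventilated patients goes with higher 6-month mortality. On the protocol's own account, then, delirium is linked to both exposure and outcome. A model that knows only about delirium in the first 24 hours treats a patient who becomes delirious later as not delirious. Part of the mortality difference that belongs to later delirium is then credited to haloperidol. Severity beyond age, dialysis, shock and ventilation can act the same way if sicker patients are more often treated.

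A second problem depends on coding. A patient must survive to the first dose to be counted as treated. If haloperidol is entered as ever/never in an analysis that starts at admission, that guaranteed survival time makes the drug look protective.

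The result is to be tested at the two-sided 5% level and described as an independent predictor of death. A drug with no effect could therefore be reported as harmful or as protective. Section 2.1 says the study should help in designing trials of haloperidol's benefit and harm.

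**Working it through.** **Figures in the plan.** The protocol gives no figure for this model. It gives two planning values that can anchor an illustration: 13% treated with haloperidol and 30% dead at 90 days (section 7.1). The interval stated for the first reproduces: 0.13 ± 1.96 × √(0.13 × 0.87 / 1000) = 0.13 ± 0.021, or 10.9% to 15.1%, against the stated 11% to 15%. I read the 13% as a share of all patients. Only the 30% point value is used below, not its stated interval.

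**Passages side by side.** Exposure may start on any ICU day (4.3.1), follow-up for death starts at admission (4.3.2), and the delirium term stops at 24 hours (7.3). Delirium that begins after 24 hours and leads to haloperidol therefore has no covariate. This holds however haloperidol is coded.

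**Illustration 1: later delirium and coding.** The true haloperidol effect is set to none. Assumptions, not from the documents:

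- 200,000 patients; lognormal ICU stay with median 4 days and sigma 0.9
- delirium in 10% on day 1, then 7% per day in ICU
- 45% of delirious patients treated, 0 to 2 days after onset
- a falling daily hazard giving 30% to 32% mortality

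The first results column is a logistic odds ratio; the others are daily Mantel-Haenszel rate ratios.

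| Assumed delirium hazard ratio for death | Ever/never haloperidol, 24-h delirium | Time-updated haloperidol, 24-h delirium | Both time-updated |
|---|---|---|---|
| 1 | 0.79 | 1.01 | 1.02 |
| 1.5 | 1.05 | 1.26 | 1.01 |
| 2 | 1.30 | 1.46 | 1.01 |

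The first row isolates immortal time. The third column shows that updating haloperidol alone does not help when later delirium affects death. The middle row shows that the two biases can nearly cancel under ever/never coding.

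**Illustration 2: severity and coding.** Cox models from admission, 40,000 patients per scenario, 13% treated, true hazard ratio 1, mean ICU stay 8 days (assumed).

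- *No severity confounder; mean start of haloperidol 2 to 7 days; 30% to 70% of deaths in the first 10 days:* ever/never 0.71 to 0.98; time-dependent 0.96 to 1.05.
- *With a severity confounder; mean start 4 days; half of deaths in the first 10 days; log hazard ratio for death 0.5 to 0.7 and log odds ratio for treatment 0.3 to 0.8 per standard deviation; mortality 32% to 34%:*

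| Coding of haloperidol | Severity left out | Severity included |
|---|---|---|
| Ever/never | 0.92 to 1.21 | 0.81 to 0.83 |
| Time-dependent | 1.10 to 1.46 | 0.96 to 1.00 |

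Only the cell with both corrections returns about 1. Adding a severity score while keeping ever/never coding leaves a spurious protective effect.

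**The case against.** The strongest reply is that much of this depends on how the model is coded, and the protocol does not fix that. The wording "between patients who receive haloperidol and patients who do not receive haloperidol" belongs to the comparison of baseline characteristics, not to the mortality model. The mortality sentence ends with "delirium in the first 24 h of admission) and time", and that last term is absent from the otherwise parallel sentence on risk factors for haloperidol use. It could mean survival time or a time-dependent term, and a statistical analysis plan may settle it. This stands. A reader might infer that the protocol treats haloperidol as if it were known at baseline, but the text does not say so. Immortal-time bias is a conditional part of this point.

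The simulations rest on assumed inputs and do not include the listed covariates, which capture part of severity. The severity variable in the second is generic; it is not SAPS II given age, dialysis, shock and ventilation. Some later-delirious patients receive no haloperidol and sit in the comparison group, so the drug term absorbs only part of the delirium effect. Section 6.1 also records prophylactic use, so not all haloperidol follows delirium. One scenario is close to null (1.05). All this stands, and it rules out any statement of expected size.

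Section 7.3 also plans exploratory analyses of the interaction between delirium and haloperidol use. These do not repair the named model, whose covariate list is fixed.

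Finally, the aim and primary outcome are descriptive, and the haloperidol–mortality association is not a listed outcome. Section 2.1 asks for knowledge of current use, not for this coefficient. This limits the weight of the point.

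**Conclusion.** The point holds for what section 7.3 fixes. The only delirium term stops at 24 hours although exposure can begin later, and the collected severity score is left out. Later delirium and residual severity therefore confound the haloperidol estimate, most plausibly towards apparent harm if delirious and sicker patients are both treated more and die more. If haloperidol is coded ever/never, immortal time is added in the opposite direction.

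The estimate can be biased either way. In the null illustrations the ever/never estimates ran from 0.71 to 1.30 across both sets of scenarios, and time-updated haloperidol without full control of delirium or severity from 1.01 to 1.46. These show the mechanism under assumed timing, delirium and severity effects; size and net sign for this study cannot be derived from the documents. A reader might conclude that the estimate must be badly wrong, or that its sign can never be read. That goes too far, because the biases can partly cancel and the coding is open.

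The descriptive primary result is untouched. This should be corrected because it is cheap and the analysis is not yet fixed beyond repair.

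**What to change.** Reword the mortality analysis in section 7.3 as follows, making the changes together:

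1. Model time to death from ICU admission, and say what the time term means.
2. Enter haloperidol as a time-dependent exposure from first dose, or use a landmark analysis among patients alive at a stated day.
3. Replace first-24-hour delirium with delirium status up to haloperidol start, taken from the daily form (for patients not yet treated, status to date).
4. Add SAPS II to the listed covariates.
5. Report the result as an association and drop the label of independent predictor.

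The cost is rewording and a little more analysis work; no new data are needed. The limits to state are residual confounding by indication, later delirium that may itself be affected by haloperidol, and overlap of SAPS II with age. Daily delirium and haloperidol records also end at ICU discharge, or at transfer to a non-participating ICU (section 5.3). Status after that point must be carried forward, or the exposure limited to the ICU stay, and the text should say which.

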3.1 Type of study

A multicentre 14-day inception cohort study investigating the pharmacological intervention practices of delirium in acutely ill ICU patients (estimated 50 ICUs in 8 countries). The 14-day study period can be selected by sites from Marts 1st to May 30th 2016.

4. Method

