4.1 Number of subjects

We expect to include 1000 acutely ill patients admitted to the participating ICUs.

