6.2 Unit/department evaluation

24. Type of hospital (< 500 beds/500-1000 beds/ > 1000 beds)
25. Type of ICU (Medical/Surgical/Mixed/Specialised)
26. Number of ICU beds open for admission
27. Does your ICU have a general guideline/protocol for identifying delirium?
28. Does your ICU have a general guideline/protocol for interventions of delirium?
29. When do you intervene for delirium?
30. Are patient restrained in your ICU (never, sometimes, often)?
31. Average nurse to patient ratio during the day, evenings and nights.

7. Statistical Methods

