7.1 Sample size estimation

In a case control study with a simple random sampling, and an estimated treatment prevalence of delirious patients treated with haloperidol in the ICU of 13% (preliminary data at Dept. of Intensive Care 4131, Rigshospitalet, Copenhagen from May 2014), inclusion of at least **1000** patients is required to yield a 95% confidence interval of a rate of haloperidol use of 11%-15%. With expected mortality rate of 30% 1000 patients will yield a 95% confidence interval of 23% - 38% for 90-day mortality. Fifty ICUs are estimated to include this sample of patients within 14 days ¹⁵.

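### The 90-day mortality model for haloperidol has no ICU term, so between-ICU differences can be read as an effect of haloperidol

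*Protocol*

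**What the plan says.** Protocol section 7.3 sets out two multivariable models in consecutive sentences.

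- **Model for haloperidol use.** It contains patient characteristics and also "ICU characteristic (university hospital, guidelines for identifying and/or treating delirium and average staff-patient ratio".
- **Model for death.** "To assess if haloperidol is an independent predictor of 90-day mortality, we will do multivariate analysis including patient characteristics", namely "age, dialysis, shock and mechanical ventilation and delirium in the first 24 h of admission) and time". The patient list is the same, the ICU characteristics are gone, and time is added.

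No ICU, site or country term, random effect or stratification is named for the mortality model anywhere in the protocol. Section 3.1 foresees an "estimated 50 ICUs in 8 countries". Section 6.2 records, for each unit, "Type of ICU (Medical/Surgical/Mixed/Specialised", hospital size, whether delirium guidelines exist and when the unit intervenes. Section 7.3 also plans exploratory analyses of delirium, haloperidol and patient outcomes, again without an ICU term.

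**The concern.** A factor that drives exposure and is also related to the outcome is a confounder. The plan itself treats features of the ICU as possible drivers of exposure, then leaves the ICU out of the one model in which haloperidol is the exposure and death the outcome.

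The patient adjustment may not close the gap. Section 6.1 collects SAPS II, sepsis, trauma and surgical status, but 7.3 puts none of them in the mortality model. Early delirium, which is in the model, is recorded with whichever instrument each site uses. ICU differences in severity and ascertainment could therefore remain.

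If they do, and if they go together with haloperidol use, the analysis could call haloperidol an independent predictor of death, or of survival, when within any one ICU it is neither. This is bias in the estimate. A standard error corrected for clustering does not remove it.

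**Working it through.** **Inputs from the protocol.** 1000 patients (4.1: "We expect to include 1000 acutely ill patients admitted to the participating ICUs") and about 50 ICUs (3.1), so 1000 / 50 = 20 patients per ICU. Haloperidol use is 13% and 90-day mortality 30% (both 7.1). Tests are two-sided at 5% (7.3).

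**The plan's own figure first.** Section 7.1 says that 1000 patients give 11% to 15% around 13%. The check is 0.13 ± 1.96 × √(0.13 × 0.87 / 1000) = 0.13 ± 0.021, or 10.9% to 15.1%. It reproduces and is not in dispute; it only confirms the setting. The 30% is used as an input alone, and nothing here relies on the interval printed beside it.

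**Assumptions, not in the protocol.** For patient i in ICU j with one measured patient covariate x (standard normal):

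- logit P(haloperidol) = α + a_j + 0.5x
- logit P(death) = β + b_j + 0.5x

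Haloperidol does not enter the second line, so the true odds ratio is 1. The ICU effects a_j and b_j are normal with SDs s_H and s_M and correlation ρ. Because b_j is independent of x, s_M is the ICU variation in mortality left after patient adjustment. α and β are set to give 13% and 30%. Section 7.3 does not name the model type; logistic regression serves as illustration.

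**What the SDs mean.** logit(0.13) = -1.90. One SD either side is 5% to 29% use for s_H = 1.0, and 8% to 20% for s_H = 0.5. logit(0.30) = -0.85. One SD either side is 24% to 37% mortality for s_M = 0.3, 22% to 39% for 0.4, and 19% to 44% for 0.6.

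**Models compared**, 1000 simulated studies per row. Model A has haloperidol and x, as planned. Model B adds the ICU's haloperidol proportion, with cluster-robust errors. The odds ratio is the exponential of the mean log odds ratio.

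| s_H | s_M | ρ | OR, A | Rejects, A | Rejects, A with cluster-robust SE | OR, B | Rejects, B |
|---|---|---|---|---|---|---|---|
| 0.5 | 0.3 | -0.5 | 0.922 | 5.7% | 6.5% | 0.989 | 5.5% |
| 0.5 | 0.3 | 0 | 0.999 | 5.5% | 5.8% | 0.999 | 6.4% |
| 0.5 | 0.3 | 0.3 | 1.033 | 4.3% | 5.1% | 0.992 | 4.6% |
| 0.5 | 0.3 | 0.5 | 1.063 | 7.4% | 8.7% | 0.990 | 6.6% |
| 1.0 | 0.4 | -0.5 | 0.838 | 12.3% | 12.5% | 0.990 | 5.9% |
| 1.0 | 0.4 | 0 | 0.981 | 5.6% | 5.0% | 0.980 | 4.9% |
| 1.0 | 0.4 | 0.3 | 1.106 | 7.3% | 7.4% | 1.000 | 5.0% |
| 1.0 | 0.4 | 0.5 | 1.177 | 16.2% | 14.9% | 0.995 | 5.6% |
| 1.0 | 0.6 | -0.5 | 0.771 | 20.8% | 18.6% | 0.985 | 4.6% |
| 1.0 | 0.6 | 0 | 0.991 | 6.0% | 6.3% | 0.991 | 6.1% |
| 1.0 | 0.6 | 0.3 | 1.150 | 13.1% | 11.6% | 0.999 | 5.6% |
| 1.0 | 0.6 | 0.5 | 1.268 | 24.0% | 21.8% | 0.993 | 5.7% |

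Simulation error on a 5% rejection rate is about 1.96 × √(0.05 × 0.95 / 1000) = 1.4 percentage points.

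**Reading.** Model A is biased only where ρ differs from zero, and the sign of ρ sets the direction. Cluster-robust errors leave up to 21.8% false positives. Model B stays at 0.98 to 1.00 in every row.

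**The case against.** **Nothing shows that the bias exists.** A reader might infer that haloperidol use and mortality are known to differ between these ICUs, and that the planned coefficient will therefore be wrong. The documents do not support that. They give no between-ICU figure for either quantity, and the haloperidol-use model only asks whether ICU features matter. Variation in both would still not be enough, because the two must be correlated after patient adjustment. This objection stands and limits the claim to what can happen.

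**The listed covariates may absorb the ICU differences.** This stands in part. In a further set of runs (400 per scenario), a measured severity covariate carried none, half or all of the ICU mortality effect. With SDs 1.0 and 0.4 and correlation 0.5, the odds ratio was 1.16, 1.07 and 0.99, with 13%, 7% and 3% rejection. The table above therefore applies to whatever ICU variation remains. How much remains is unknown, but the list omits SAPS II and admission type.

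**Handling of centre belongs in a statistical analysis plan.** Often it does, and model type and link can fairly wait. Here, however, the protocol writes out the covariate list, and it differs from the list one sentence earlier precisely in dropping the ICU.

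**The study is descriptive.** True: the primary outcome is a count, and section 2.1 ties the design of later trials to knowledge of current use, not to this association. A reader might infer that the later randomised trial would be misdirected; the protocol does not support so strong a consequence. The mortality analysis is nevertheless a named inferential aim tested at 5%.

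**Conclusion.** The mortality model as written leaves confounding by ICU uncontrolled, although the plan itself treats ICU features as candidate drivers of haloperidol use. Whether this distorts the result depends on a correlation that the protocol does not report.

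For SDs of 1.0 and 0.4 to 0.6 and correlations of -0.5 to 0.5, a null effect shows as an odds ratio of about 0.77 to 1.27, with up to about 25% false positives. For SDs of 0.5 and 0.3 it shows as 0.92 to 1.06, with rejection close to nominal (4% to 7%). At zero correlation there is no material bias. The SDs and correlations are assumptions throughout.

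This is a worthwhile correction to a secondary analysis. It does not touch the primary outcome or the other descriptive results.

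**What to change.** Add one sentence to section 7.3: the association of haloperidol with 90-day mortality will be estimated within ICUs. There are two ways to do so:

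1. Enter the ICU's haloperidol proportion beside the patient's own exposure, with a random ICU effect or cluster-robust errors.
2. Stratify or condition on ICU (stratified Cox or conditional logistic regression).

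Apply the same to the exploratory outcome analyses. Cluster-robust errors alone do not remove the bias. A random intercept alone removes only part of it, because it still mixes between-ICU with within-ICU information. Adding only the three ICU characteristics from the haloperidol-use model may not be enough.

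**Cost.** No new data are needed, since the ICU of each patient is known. The standard error of the log odds ratio rises by about 5% to 10% (for example 0.20 to 0.22, and 0.22 / 0.20 = 1.10). Under option 2, ICUs with no haloperidol users (about 20% of them at a haloperidol SD of 1.0) or with no deaths do not contribute. Option 1 keeps all ICUs in the model. Neither option deals with confounding between patients inside the same ICU, so the result remains an association.

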Give a score of "1" to each of the 8 items below if the patient clearly meets the criteria defined in the scoring instructions. Give a score of "0" if there is no manifestation or unable to score. If the patient scores ≥ 4 , notify the physician. The diagnosis of delirium is made following clinical assessment; document in the Assessment and Intervention record (RN) and progress note (MD).

Assessment	Scoring Instructions	Score
1. Altered Level of Consciousness*	
 If MASS portion of VAMASS is 0 (no response) or 1 (response to noxious stimulus only), record "U/A" (unable to score) and do not complete remainder of screening tool Score "0" if MASS score is 3 (calm, cooperative, interacts with environment without prompting) Score "1" if MASS score is 2, 4, 5 or 6 (MASS score of 2 is a patient who only interacts or responds when stimulated by light touch or voice – no spontaneous interaction or movement; 4, 5 and 6 are exaggerated responses) 	
If MASS \neq 0 or 1, screen items 2-8 and complete a total score of all 8 items.		
2. Inattention	"1" for any of the following: 
 Difficulty following conversation or instructions Easily distracted by external stimuli Difficulty in shifting focuses 	
3. Disorientation	"1" for any obvious mistake in person, place or time	
4. Hallucination/ delusions/ psychosis	"1" for any one of the following: 
 Unequivocal manifestation of hallucinations or of behaviour probably due to hallucinations (e.g. catching non-existent object) Delusions Gross impairment in reality testing 	
5. Psychomotor agitation or retardation	"1" for any of the following: 
 Hyperactivity requiring additional sedatives or restraints in order to control potential dangerousness (e.g. pulling out IV lines, hitting staff) Hypoactivity or clinically noticeable psychomotor slowing (differs from depression by fluctuation in consciousness and inattention) 	
6. Inappropriate speech or mood	"1" for any of the following (score 0 if unable to assess): 
 Inappropriate, disorganized or incoherent speech Inappropriate display of emotion related to events or situation 	

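### The only brain-state covariate in both section 7.3 models is first-24-hour delirium, which cannot be assessed in comatose or deeply sedated patients; the protocol does not say how they enter it and uses its coma data in neither model

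*Protocol*

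**What the plan says.** Section 7.3 of the protocol names the covariates of two models. The model for haloperidol use is described as "multivariate analyses including patient characteristics (age, dialysis, shock and mechanical ventilation and delirium in the first 24 h of admission) and ICU characteristic", followed by the ICU characteristics. The model asking whether haloperidol independently predicts 90-day mortality is a "multivariate analysis including patient characteristics (age, dialysis, shock and mechanical ventilation and delirium in the first 24 h of admission) and time". Neither list contains coma, depth of sedation, unable-to-assess status or SAPS II.

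The delirium tools do not return a valid negative in an unresponsive patient:

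- Section 6.1, item 12a, has three recording levels: "CAM-ICU (positive /negative/UTA, Unable To Assess").
- Appendix 3, ICDSC item 1, tells the assessor at MASS 0 or 1 to record U/A ("unable to score) and do not complete remainder of screening tool").
- The DOS form in Appendix 3 has columns for unable that carry no score.
- The behavioural criterion in section 4.3.2, secondary outcome 2, carries a GCS above 7.

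Section 6.1 records deep sedation daily in item 10 ("one score equals one positive day with sedative induced coma") and GCS below 8 without sedation in item 11.

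Three rules bear on coding, and they do not agree. Section 6.1, item 12, counts positives only ("one positive score equals one delirium day"). The general ICDSC instruction gives a 0 "if there is no manifestation or unable to score". Secondary outcome 4 in section 4.3.2 accepts a day as delirium-free only when every assessment in the 24 hours was negative.

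**The concern.** A patient who is comatose or deeply sedated for the whole first 24 hours has no valid delirium result. If the covariate has two levels and that patient is coded as not delirious, the reference group pools awake patients who were assessed and found negative with patients who could not be assessed.

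If the unassessable patients also differ in later haloperidol use and in mortality, early coma is an unadjusted common cause of both. Part of its effect is then credited to haloperidol in the mortality model. In the use model haloperidol is the outcome, so the estimate at risk there is the delirium coefficient, whose reference group is mixed.

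The protocol separates coma from delirium in secondary outcome 4 and collects the data to do so, but the models do not use that distinction.

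**Working it through.** **1. Possible codings.** The protocol gives no rule for an unassessable patient in this covariate. With two levels there are three options:

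| Coding of unassessable patients | Consequence |
|---|---|
| No delirium | Reference mixes assessed-negative and comatose patients |
| Delirium | Coma is labelled as delirium |
| Missing | A complete-case model drops comatose patients |

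Under the all-negative rule of secondary outcome 4, such a patient is neither delirious nor delirium-free, which calls for a third level.

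**2. Size if coded as no delirium.** No figure in the protocol attaches to this point, so every rate below is an assumption. The method is logistic regression on expected cell frequencies, with cell weight = P(state) × P(ventilated | state) × P(haloperidol | state) × P(death or survival). The true haloperidol effect on death is nil (OR 1.00). Two models are compared:

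- two-level: logit P(death) = b0 + b1·delirium + b2·ventilation + b3·haloperidol
- three-level: the same plus a coma/unassessable term

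*Set A.* First-24-hour states: coma 20% or 40%, delirium 20%, remainder neither. Mortality 45% / 30% / 12% and ventilation 90% / 40% / 30% (coma / delirium / neither). Haloperidol use 35% with delirium, 4% with neither, and varied after coma. Haloperidol-mortality OR from the two-level model:

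| Haloperidol use after coma | Coma 20% | Coma 40% |
|---|---|---|
| 2% | 0.94 | 0.93 |
| 4% (same as neither) | 1.00 | 1.00 |
| 10% | 1.15 | 1.15 |
| 20% | 1.37 | 1.31 |
| 30% | 1.55 | 1.44 |

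With a smaller mortality contrast (35% / 30% / 20%) and 10–30% use after coma, the range is 1.06–1.21. If half of the coma patients are counted as delirious through the restraint criterion, 10–30% use after coma gives about 1.0 to 1.3.

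*Set B.* Coma 10–40%; delirium in 15% of the rest. Haloperidol use 40% with delirium, 6% with neither, 3–25% after coma. Ventilation 90% in coma, 30% otherwise. Death: baseline 20%, OR 1.8 for ventilation, 1.5 for delirium, 1 to 3 for coma. The two-level model gives 0.92–1.29. It gives exactly 1.00 when use after coma is 6% or when the coma-death OR is 1.

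The three-level model gives 1.00 in every scenario of both sets.

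**3. Delirium coefficient in the use model.** Set A, unadjusted, 20% use after coma. Against assessed-negative patients the OR is (0.35/0.65) / (0.04/0.96) = 12.9. With the merged reference:

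- coma 20%: use = (0.20×0.20 + 0.60×0.04)/0.80 = 8%; OR = (0.35/0.65)/(0.08/0.92) = 6.2
- coma 40%: use = (0.40×0.20 + 0.40×0.04)/0.80 = 12%; OR = (0.35/0.65)/(0.12/0.88) = 3.9

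Set B, adjusted for ventilation, gives 5.2 to 12.7 instead of 10.4, so this distortion can also go either way.

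**4. Effect on the test.** Take N = 1000, 13% haloperidol use and 30% mortality from section 7.1, giving 130 users and 870 non-users. The unadjusted standard error of the log OR is √[1/(130×0.3×0.7) + 1/(870×0.3×0.7)] = 0.205. A spurious OR of 1.15 shifts z by ln(1.15)/0.205 = 0.68, and the nominal 5% two-sided error becomes about 10%. An OR of 1.29 shifts z by 1.24, and it becomes about 24%.

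**The case against.** The strongest objection is that the text does not contain the premise. Section 7.3 does not say that the covariate is yes/no, or that unassessable patients are coded as not delirious. The all-negative rule in secondary outcome 4 and the separate UTA and U/A levels point the other way. Covariate coding is commonly left to a statistical analysis plan, which is not shown. This stands against any claim that the plan makes this coding error. It does not remove the point, because section 7.3 itself fixes the covariate list, and that list has no coma or sedation term.

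A reader might infer that the sickest patients necessarily join the reference group. The documents do not support that: being restrained to the bed counts as delirium without any score, so some sedated patients may be classed as delirious.

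A reader might also infer that the mortality estimate is biased towards harm. That needs higher haloperidol use after coma than in assessable patients without delirium, and the protocol gives no such rate. Lower use after coma reverses the direction.

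Two further limits stand. The illustrations adjust for ventilation only, whereas section 7.3 also includes age, dialysis and shock, which may carry part of the same severity. And the return to 1.00 with three levels follows from how the scenarios were built. Finally, the aim is descriptive and the primary outcome is a count, so these models are supporting analyses.

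**Conclusion.** The concern holds in a limited form. Both models fix first-24-hour delirium as the only brain-state covariate. The protocol's tools cannot assess it in unresponsive patients, the coding of those patients is not stated, and no two-level coding represents them properly. Coma and sedation data are collected and used in neither model.

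If unassessable patients are coded as not delirious, confounding by early coma is possible. On assumed rates with no true effect, the haloperidol-mortality OR runs from about 0.9 to 1.55. Neither size nor direction is established: both depend on haloperidol use and mortality after coma, and the bias is nil if either equals that in assessable patients without delirium after adjustment. In the use model only the delirium coefficient is at risk. The change is worth making because it is cheap and the mortality model is meant to support a statement about an independent association.

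**What to change.** In both section 7.3 models, replace first-24-hour delirium by a three-level state:

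1. delirious (any positive assessment);
2. coma, deep sedation or otherwise unassessable, with no positive assessment (items 10 and 11, or UTA, U/A or unable under item 12);
3. assessed and negative, as the reference.

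Alternatively, keep the delirium term and add a first-24-hour coma/unassessable indicator.

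State the coding in section 7.3 and make it consistent with secondary outcomes 2 and 4 in section 4.3.2, with section 6.1, item 12, and with the ICDSC instruction to score 0 when unable. Say how restraint to the bed counts in a comatose patient. Items 10 and 11 flag coma at any time in a day, so also say where a patient goes who was deeply sedated for part of the period and assessed negative in another part.

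The cost is one extra parameter per model and a wording change, with no new data. With the three-level version, patients both comatose and delirious sit in the delirious level, so some coma confounding remains there.
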